1.1.3 Mucolox™

Mucolox™ is a mucoadhesive polymer gel that can be used in pharmaceutical compounding for the management of diseases and conditions of the oral mucosa including oral mucositis, and mouth ulcers^{29,30}. The safety and toxicological profile of Mucolox™ was evaluated in vitro and compared to Triton X- 100 (positive control) and distilled water (negative control), using a 3-

dimensional model of the human oral mucosa. Results showed that Mucolox™ can bind to tissues six times longer than Triton X-100 (before 50% cell viability) therefore offering increased retention of medication at the site of action. Additionally, at 4.5 hours, the difference in percent cell viability between Mucolox™ and distilled water was not significant, making it a safe water-soluble mucosal delivery system.

A recent study from our group showed that commercial dexamethasone 0.5mg/5mL solution compounded with Mucolox™ was found to be a safe option for the management of oral lichen planus when rinsed three times a day for 5-minute swish and expectorate³¹. Subjects receiving dexamethasone 0.5mg/5mL solution in Mucolox™ had a better clinical response compared to dexamethasone 0.5mg/5mL commercial solution alone (6-point reduction vs. 4.3; $p < 0.001$) of reticulation/keratosis, erythema, and ulceration (REU) scores. Both arms had a subjective improvement of the oral symptoms after 4 weeks of treatment.

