2.1.2 Potential benefits for participating individuals

All subjects will be assigned an active treatment. Thus, it is anticipated that the majority of participants may benefit from participation in this study. Additionally, most participants may benefit from the satisfaction in knowing that their involvement has a potential impact on the clinical care of future patients suffering from their condition.

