3.2 Secondary Objectives

The secondary objectives are:

- To determine the clinical improvement in clinician-reported outcome measures achieved by treatment with topical compounded dexamethasone at 0.5 mg/5 mL in Mucolox™ compared to commercial dexamethasone 0.5mg/5ml solution alone.
- To assess the tolerability of Oral Inflammatory Ulcerative Diseases as measured with the 14-item Oral Health Impact Profile (OHIP-14).

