13.1.1 Analysis of Primary Endpoints

VAS scores will be summarized descriptively for each arm at pre-treatment, post-treatment, and pre-to-post treatment change. The pre-to-post treatment change will be compared between the arms using either Student's t-test or Mann-Whitney test, depending on the distribution of the data.

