13.1.2 Analysis of Secondary Endpoints

Oral health related quality of life will be assessed before and after topical therapy using the 14-item Oral Health Impacts Profile (OHIP-14; see Appendix 5) instrument that measures subject's perceptions of the impact of oral conditions on their well-being. The OHIP-14 scores will be summarized descriptively for each arm at pre-treatment, post-treatment, and pre-to-post treatment change. The pre-to-post treatment change for each item and for all items combined will be assessed within each arm using either paired t test or Wilcoxon-signed-rank test depending on its distribution. In addition, each question will be dichotomized and classified as 'response' if the answer is 'not at all', or 'slightly' to a question such as "how isolated do you feel as a result of this oral condition", and pre-to-post treatment improvement will be assessed using McNemar's test within each arm.

In order to evaluate the clinical improvement in clinician-reported outcome measures for Oral Inflammatory Ulcerative Diseases, REU scores within the compound dexamethasone solution in Mucolox™ group (Arm A) will be compared to that in the dexamethasone solution only group (Arm B). The REU scores will be summarized descriptively for each arm at pre-treatment, post-treatment, and pre-to-post treatment change. The pre-to-post treatment change will be compared between the arms using either student's t-test or Mann-Whitney test, depending on the distribution of the data.

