Appendix 1**INSTRUCTIONS FOR PREPARING & USING YOUR
TOPICAL SOLUTION****WHAT YOU WILL RECEIVE**

- One 480 mL bottle of concentrated solution (5 mg/5 mL)
- 4 tablets of fluconazole 200 mg

USING YOUR SOLUTION

You will be rinsing with your solution **3 times per day**.

1. Gently shake the bottle of solution.
2. Pour 5 mL of solution into the dosing cups provided.
3. Swish the solution in your mouth for 5 minutes, then spit – DO NOT SWALLOW!
4. Do not eat or drink for 15 minutes after rinsing.

Please take one table of fluconazole once a week

CONFIDENTIAL

This document is confidential. Do not disclose or use except as authorized.

	11													
	12													
	13													
	14													

	3													
	15													
	16													
	17													
	18													
	19													
	20													
	21													
	22													
	4													

CONFIDENTIAL

This document is confidential. Do not disclose or use except as authorized.

	23																						
	24																						
	25																						
	26																						
	27																						
	28																						

CONFIDENTIAL

This document is confidential. Do not disclose or use except as authorized.

Appendix 3

DEXAMETHASONE RINSE IN MUCOLOX™ FOR THE TREATMENT OF ORAL INFLAMMATORY ULCERATIVE DISEASES

VISIT #1

Subject Name _____

[figure not shown]
[figure not shown]
Medical Record Number _____

Date of Visit _____

SUBJECTIVE DATA (Over last two weeks unless specified)

MUCOSAL PATHOLOGY

- 1. Does your mouth hurt now? Y/N
- 2. Does it hurt to swallow food or drink? Y/N
- 3. How would you rate your worst mouth sensitivity over the last week?

No sensitivity

Worst sensitivity

CONFIDENTIAL

This document is confidential. Do not disclose or use except as authorized.

[figure not shown]
[figure not shown]
4. Do you avoid any foods because they make your mouth hurt?

- 0 = Not at all
- 1 = Slightly
- 2 = Moderately
- 3 = Quite a bit
- 4 = Extremely

If “yes”, what types of foods?

- a. Spicy foods
- b. Acidic foods
- c. Salty foods
- d. Hard/crunchy/crusty foods
- e. Other:

5. Do you feel that your oral intake (what you eat) is limited by your oral condition? Y/N

Not limited at all

Severely limited

Score: _____

If “Yes”, how limited do you feel it is?

- a. Partial limitation
- b. Severe limitation

6. Have you been bothered by ulcers in the mouth?

- 0 = Not at all
- 1 = Slightly
- 2 = Moderately
- 3 = Quite a bit
- 4 = Extremely

CONFIDENTIAL

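### The OHIP-14 response rule uses answer labels and an example item that are not on the Appendix 5 form, and OHIP-14 change is tested only within arms while VAS and REU changes are compared between arms.

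*Combined protocol and SAP*

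**What the plan says.** **The response rule.** Section 13.1.2 names the OHIP-14, refers to Appendix 5, and states that "each question will be dichotomized and classified as 'response' if the answer is 'not at all', or 'slightly' to a question such as" the example "how isolated do you feel as a result of this oral condition". Response is then tested by McNemar's test within each arm.

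**The form.** Appendix 5 has 14 items, each answered Never (0), Hardly Ever (1), Occasionally (2), Fairly Often (3) or Very Often (4).

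**The change tests.** In 13.1.2 the OHIP-14 change "for each item and for all items combined will be assessed within each arm", by paired t or Wilcoxon signed-rank test. By-arm descriptive summaries are also planned. For the VAS, section 13.1.1 says: "The pre-to-post treatment change will be compared between the arms using either Student's t-test or Mann-Whitney test". Section 13.1.2 plans the same between-arm comparison for the REU score. No section gives a between-arm estimate, interval or test for the OHIP-14.

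**The objectives.** In section 3.2 the clinician-reported objective names the commercial solution as comparator. The OHIP-14 objective names none.

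**The concern.** There are two separate problems.

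First, the rule and the form do not match. A programmer with Appendix 5 data would find no answer carrying either response label and would have to choose a cut-off. In an open-label trial (section 8.2), that choice should be on paper before the data are seen.

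Second, the only OHIP-14 inference planned is pre to post within an arm, and the protocol gives reason to expect gains in both arms. Section 2.1.2 says "All subjects will be assigned an active treatment", and section 1.1.3 reports of the preliminary study that "Both arms had a subjective improvement of the oral symptoms after 4 weeks of treatment". Improvement within an arm mixes the effect of dexamethasone, the course of the disease, regression from a high entry score (worst sensitivity of at least 7) and any effect of the vehicle. Only the randomised contrast isolates the vehicle. As planned, the trial can report that quality of life improved, but it has no specified analysis of whether Mucolox contributed.

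**Working it through.** **1. Rule against form**

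| | Section 13.1.2 | Appendix 5 |
|---|---|---|
| Answers | *not at all* or *slightly* count as response | *Never*, *Hardly Ever*, *Occasionally*, *Fairly Often*, *Very Often* (0-4) |
| Example item | feeling isolated | none of the 14 items |

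The labels in the rule do appear on the visit CRFs (Appendices 3 and 4), at item 4 on avoiding foods and at item 6, "Have you been bothered by ulcers in the mouth". Neither belongs to the OHIP-14, and the isolation item is not on the CRFs either. Both scales run from 0 to 4 and the rule takes the two lowest levels, so the natural counterpart on Appendix 5 is 0-1. The plan does not say so.

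**2. Count of planned OHIP-14 tests**

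- Paired tests that can be run: (14 items + 1 total) × 2 arms = 30.
- McNemar tests that cannot be run as literally written: 14 × 2 = 28.
- Between-arm tests: 0.

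**3. What the within-arm tests can show**

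Inputs: 15 per arm and two-sided 5% (section 13.2). The documents give no OHIP-14 effect size or SD, so the standardised pre-to-post change dz is an assumption, shown over a range. Method: paired t-test, power p from the noncentral t with 14 degrees of freedom and noncentrality dz × √15, arms independent. With equal true gains, P(exactly one arm significant) = 2p(1 − p) and P(both) = p².

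| dz, both arms | p | exactly one arm | both arms |
|---|---|---|---|
| 0.3 | 0.192 | 0.31 | 0.04 |
| 0.5 | 0.438 | 0.49 | 0.19 |
| 0.78 | 0.802 | 0.32 | 0.64 |
| 1.0 | 0.949 | 0.10 | 0.90 |
| 1.2 | 0.991 | 0.02 | 0.98 |

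At small to moderate gains, a split result is common when the arms do not differ. At large gains both arms are significant whether or not the vehicle adds anything. Let Mucolox add a further 1.06 SD of change in arm A:

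- Arm B at 1.0: both arms are significant with probability 0.949² = 0.90 if Mucolox adds nothing, and 0.949 × 1.00 = 0.95 if it adds 1.06 SD.
- Arm B at 1.2: the corresponding values are 0.98 and 0.99.

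**4. What a between-arm comparison would give**

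- Two-sample t-test of change, two-sided 5%, 80% power: detectable difference 1.06 SD with 15 per arm. With the 5% loss in section 13.2, 15 × 0.95 = 14.25; with 14 per arm it is 1.10 SD.
- 95% CI half-width = t(0.975, 2n − 2) × √(2/n). For n = 15: 2.048 × 0.365 = 0.75 SD. For n = 14: 2.056 × 0.378 = 0.78 SD.
- Adjusting week-4 score for baseline instead of using change, with equal SDs and baseline to week-4 correlation r, multiplies the half-width by √((1 + r)/2) (the lost degree of freedom is ignored). At assumed r = 0.3, 0.5 and 0.7 this is 0.81, 0.87 and 0.92, so 8% to 19% narrower.

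**The case against.** The strongest reply is that the analysis follows the objectives. The REU objective is comparative and the REU is compared between arms; the OHIP-14 objective only asks for assessment, and within-arm tests assess. Nothing in the protocol proposes to infer an arm difference from one significant and one non-significant result, so the split-result probabilities describe a misreading nobody has planned. The added comparison would be weak: by the same two-sample t calculation, power with 15 per arm is about 12%, 26% and 56% at differences of 0.3, 0.5 and 0.8 SD. The outcome is patient-reported and open label, so expectation bias would remain. A reader could derive a crude difference if the by-arm summaries give means and SDs. The label mismatch is a slip in a supplementary analysis, and section 13 promises a later SAP that could settle both points.

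Much of this is fair. The missing comparison does not contradict the OHIP-14 objective; it is a missed use of the randomisation. The label error leaves the total score and the 30 paired tests untouched. Moving from intensity labels to frequency labels is also not a pure translation, so the 0-1 cut-off needs the sponsor's confirmation.

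The conclusion still stands. The OHIP-14 is a named secondary endpoint of a randomised trial of two active arms, and its only planned inference cannot speak to the vehicle. An imprecise randomised difference with its interval addresses that question; a within-arm p-value does not. Section 13 allows changes in the later SAP but commits to none here.

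**Conclusion.** Both parts hold. The response rule is wrong as written: 28 planned McNemar tests have no usable definition on the Appendix 5 form, although one natural correction exists. Separately, the plan has no between-arm OHIP-14 estimate, interval or test. The within-arm tests it has would split the arms by chance 31% to 49% of the time at assumed gains of 0.3 to 0.5 SD, and would hardly discriminate at gains of 1.0 SD or more.

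The text comparison needs no assumption. The probabilities assume normal changes, independent arms, 15 per arm and standardised gains that the documents do not supply.

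This should be corrected, but it is not critical: a secondary endpoint is affected, and the primary VAS comparison is not.

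**What to change.** In section 13.1.2:

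1. Define response as an answer of Never or Hardly Ever (0-1), confirmed by the sponsor before any outcome data are examined. Replace the isolation example with an Appendix 5 item, such as the one on difficulty relaxing. Label the dichotomised analysis descriptive.
2. Add: *The week-4 OHIP-14 total (0-56) will be compared between arms with adjustment for the baseline total, and reported as a difference with its 95% CI.* At minimum, apply to the OHIP-14 total the between-arm comparison of change already planned for VAS and REU, with the difference and 95% CI.
3. Report the within-arm OHIP-14 results as descriptive.

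In the synopsis statistics row, the McNemar sentence stands under the primary analysis plan without naming an endpoint. Tie it to the OHIP-14 as a secondary analysis. Carry all changes into the SAP promised in section 13.

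The cost is wording only. Section 9.2.2 already has patients complete the OHIP-14 at baseline and at the end of treatment. The between-arm estimate will be imprecise (unadjusted half-width 0.75 to 0.78 SD of change) and may carry expectation bias because the trial is open label; the report should say both. The within-arm p-values lose their inferential role.

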13.2 Sample Size, Accrual Rate and Study Duration

The sample size was calculated based on the data by Rhodus et al., as to ensure at least 80% power and two-sided alpha of 0.05 in detecting a t difference of 2.0 points oral pain on an 11 point scale (VAS 0-10) between Arm A and B²⁷. The mean expected change for Arm A will be 6.5 points reduction with a standard deviation of 1.4 points. The mean expected change for Arm B will be 4.5 points reduction with a standard deviation of 1.4 points.

A total of 15 patients per arm will be enrolled (total of 30 subjects). The proposed sample size includes a loss of follow up of 5%. Approximately 60 patients per year are diagnosed with Oral Inflammatory Ulcerative Diseases at the Sol Silverman Oral Medicine Clinic at UCSF. We anticipate the accrual rate will be approximately 2 patients per month, thus the accrual goal will be achieved in approximately 15 months.

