EFFICACY EVALUATIONS	
PRIMARY ENDPOINT	
 Change from pre to post treatment in each subject's subjective sensitivity score (0-10) evaluated at baseline and 4 weeks post treatment for each arm. We will also compare changes of the daily subject's subjective sensitivity score (0-10) over time for each arm.
SECONDARY ENDPOINTS	
 The secondary endpoints include the evaluation of objective data using the REU scoring system and the oral health related quality of life using the OHIP-14.
OTHER EVALUATIONS	None
SAFETY EVALUATIONS	The safety of participants and the overall study will be monitored continuously throughout the study period. At the 4 week visit, evaluating doctors will review the participants' diaries for self-reported adverse events.
PLANNED INTERIM ANALYSES	When approximately 50% of patients have completed the study, an interim analysis for safety will be conducted by an independent data monitoring committee. Serious adverse events will be monitored by the committee on an ongoing basis throughout the study.
STATISTICS Primary Analysis Plan	Pre-to-post treatment improvement will be assessed using McNemar's test within each arm. The REU scores will be summarized descriptively for each arm at pre-treatment, post-treatment, and pre-to-post treatment change. The pre-to-post treatment change will be compared between the arms using either student's t-test or Mann-Whitney test, depending on the distribution of the data.
Rationale for Number of Subjects	The sample size was calculated to ensure at least 80% power and two-sided alpha of 0.05 in detecting a t difference of 2.0 points oral pain on an 11 point scale (VAS 0-10) between Arm A and B.

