12.4 Replacement of Subjects

Subjects who withdraw from the study treatment will be replaced.

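### Does planning 15 patients per arm, when the stated inputs need about 10, call for a correction to the sample size section?

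*Combined protocol and SAP*

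**What the plan says.** Section 13.2 (Sample Size, Accrual Rate and Study Duration) opens with "The sample size was calculated based on the data by" a cited study, which section 1.1.2 describes as 13 patients with erosive-ulcerative oral lichen planus treated with dexamethasone rinse. It sets at least 80% power at two-sided alpha 0.05 for a difference of 2.0 points between arms. The expected results are given arm by arm: "The mean expected change for Arm A will be 6.5 points reduction with a standard deviation of 1.4 points", and "The mean expected change for Arm B will be 4.5 points reduction with a standard deviation of 1.4 points". The number follows: "A total of 15 patients per arm will be enrolled (total of 30 subjects"). On attrition it adds that "The proposed sample size includes a loss of follow up of 5" per cent.

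The synopsis row on the number of subjects repeats the commitment: "The sample size was calculated to ensure at least 80% power and two-sided alpha of 0.05". Section 13.1.1 compares the pre-to-post change between arms by Student's "t-test or Mann-Whitney test, depending on the distribution of the data". On losses, section 12.4 states: "Subjects who withdraw from the study treatment will be replaced". Section 12 (Protocol Violations) also replaces patients who become unevaluable for the primary endpoint through non-compliance or new immunomodulatory treatment.

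**The concern.** Section 13.2 presents 30 patients as the result of a calculation and gives every input that such a calculation needs. A reader who repeats it gets 20. Attrition does not close the gap: the 5% is already counted, moving from 9 evaluable to 15 enrolled would take a loss of 1 - 9/15 = 40%, and most patients lost to the primary analysis are replaced anyway.

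A second question concerns the standard deviation. Section 1.1.2 reports the cited study's scores as 6.7 ± 1.4 before treatment and 2.3 ± 0.6 after, with no standard deviation of the change. The planned standard deviation of change, 1.4, has the same value as the pre-treatment one.

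If the gap reflected an error, two things could be at stake. The trial might enrol 10 more patients than it needs, about 5 months of accrual at the stated 2 per month. Or the inputs might be misreported, so that the true power is unknown.

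**Working it through.** **Inputs.** From section 13.2: difference δ = 6.5 - 4.5 = 2.0; standard deviation of change σ = 1.4 in both arms; two-sided alpha 0.05; power at least 80%; equal arms; 5% loss. The test comes from section 13.1.1.

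**1. Trying to reproduce 15 per arm at 80% power.**

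- Normal approximation: n = 2(1.960 + 0.842)² × 1.4² / 2.0² = 7.69, so 8 evaluable. Then 8/0.95 = 8.4, so 9 enrolled.
- Exact t-test (noncentral t, standardised difference 2.0/1.4 = 1.43): n = 8.76, so 9 evaluable. Then 9/0.95 = 9.5, so 10 enrolled, 20 in total.
- Mann-Whitney, t-test number divided by an assumed efficiency: 8.76/0.955 = 9.2, so 10 evaluable and 11 enrolled; 8.76/0.864 = 10.1, so 11 evaluable and 12 enrolled.
- Mann-Whitney, Noether formula: P(X > Y) = Φ(2.0/(1.4√2)) = 0.844, and n per arm = (1.960 + 0.842)² / (6 × 0.344²) = 11.07, so 12 evaluable. Then 12/0.95 = 12.6, so 13 enrolled.

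At exactly 80% power the stated inputs therefore give 9 to 13 enrolled per arm, and 15 is not reproduced.

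**2. Does 15 per arm deliver what is promised?** Five per cent of 15 is 0.75, so 14 evaluable is the cautious count.

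| Evaluable per arm | Power by t-test, δ = 2.0, σ = 1.4 |
|---|---|
| 9 | 81.2% |
| 10 | 85.5% |
| 14 | 95.3% |
| 15 | 96.5% |

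Simulated Mann-Whitney power under normal data is about 94.6% with 14 per arm and 95.2% with 15. The 80% floor is met by either test, after the stated loss.

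**3. Which ordinary choices give 15?**

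- 95% power by t-test: n = 13.8, so 14 evaluable; 14/0.95 = 14.7, so 15 enrolled.
- 90% power with an efficiency of 0.864 for Mann-Whitney: 11.35/0.864 = 13.1, so 14 evaluable and 15 enrolled.
- 80% power with σ = 1.8: n = 13.7, so 14 evaluable and 15 enrolled.

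The documents state none of these. The first two keep every stated input and go above the power floor.

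**4. How much does the source of the 1.4 matter?** With the cited study's two standard deviations and a pre-post correlation r, the standard deviation of change is √(1.4² + 0.6² - 2r × 1.4 × 0.6).

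- It equals 1.4 when r = 0.36/1.68 = 0.21.
- At r = 0 it is √2.32 = 1.52. Power for 2.0 points is then 93.5% with 15 per arm and 91.7% with 14.
- A higher correlation lowers it: 1.22 at r = 0.5.

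The documents give no value of r, so these are a range. Power for 2.0 points stays at 80% or more up to a standard deviation of change of 1.887 with 15 per arm, or 1.818 with 14. With only 9 evaluable per arm and a standard deviation of 1.52, power would be 74.4%.

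**The case for a change.** The best case for acting is that a calculation with all its inputs stated should return the stated answer. This one returns 20 against 30, and a reader cannot tell whether a higher power target, a larger standard deviation or an allowance for the rank test produced the difference. The repair is nearly free, since one paragraph and one synopsis row could report the power actually achieved. The planned standard deviation is also the weakest input, because it rests on 13 lichen planus patients while this trial also covers pemphigus, pemphigoid and chronic graft-versus-host disease. Readers would benefit from seeing how much margin 30 patients buy.

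The arithmetic in this stands: 15 per arm is not the 80% number, and the reason for it is not written down. The inference that something needs correcting does not stand. The wording sets a minimum power and never presents 15 as the smallest adequate number. The point about the standard deviation is weaker than it looks. Section 13.2 already states 1.4 openly as the planned value for change, and the idea that it was borrowed from the pre-treatment figure rests only on the two numbers matching. The wider case mix is a reason to keep the margin, and the plan already has it.

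**Conclusion.** No change is needed. The stated inputs need about 10 enrolled per arm by t-test and 11 to 13 if sized for Mann-Whitney, against 15 planned. The gap is an unstated rationale. The promise of at least 80% power is kept with about 15 percentage points to spare (95.3% with 14 evaluable per arm), no stated figure is false, and 15 per arm is what a 95% target with 5% loss yields. Cutting to 20 patients would give up protection against a larger standard deviation in a mixed-disease population. Keeping 30 costs about 5 months of accrual, with every patient on an active steroid rinse, which is a fair trade.

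This rests on roughly normal changes with equal spread in the two arms, on loss near the stated 5%, and on a standard deviation of change no larger than about 1.8, which covers every non-negative pre-post correlation on the cited study's figures. A sponsor revising section 13.2 for other reasons could add a line on the power target and the source of the 1.4. Enrolment, the analysis and the reading of the results would be the same without it.
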